## Objectives

The study aims to provide answers to the following research questions

1. Is the group therapy program feasible?
2. Is the group therapy program accepted by stroke survivors and therapists?
3. Are there first indications on the efficacy of the group therapy to improve psychopathology and/or ACT-specific outcome measures?

Feasibility is hereby assessed via quantitative and objective indicators in accordance with a previous study investigating the efficacy of ACT in people with acquired brain damage (Sathananthan et al., 2022). These indicators include recruitment rates ( $\geq 3$  participants per group within six months), drop-out rates  $\leq 20\%$ , group attendance  $\geq 80\%$  (out of 8 participants \* 8 sessions = 64), homework completion rates  $\geq 50\%$  (for each session from participants present in session), completion rates of outcome measures  $\geq 80\%$ , treatment fidelity  $\geq 80\%$  (adherence to objectives and contents listed in the manual). Fidelity ratings are based on video recordings of two randomly selected sessions. A research assistant rates the therapists' behavior according to a checklist developed for that session.

Patients rate therapy acceptance with a validated "group therapy session questionnaire" (GTS-P; Zoubek, 2013), which includes six items for each session assessing for example active involvement and comprehensibility of contents, and two items for the entire group therapy on satisfaction and prospect of success. Therapists rate therapy acceptance with a co-developed questionnaire (GTS-T) including twelve items for each session which assess the same six contents as the patients' questionnaire and additional six items on the therapist's involvement and satisfaction. Therapists also rate acceptance for the entire group therapy for each patient on six items also resembling the six items of the patient session questionnaire (GTS-TP). All items are rated on a five-point Likert scale (0 = not true at all to 4 = absolutely true). Mean ratings in a previous study investigating a group therapy for people with diabetes and depression ranged from 2.26 to 2.86 in the different versions of the questionnaire (Zoubek, 2013). Accordingly, a mean value higher than 2 is considered as adequate therapy acceptance by patients and therapists in this study.

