Preliminary efficacy is evaluated both via reducing of psychopathological symptoms and increasing of ACT-specific outcomes. ACT aims to improve psychological flexibility, which itself consists of the six processes present in the moment, acceptance, cognitive defusion, self-as-context, values and committed action (Hayes, 2016). In addition to the overall construct of psychological flexibility, the subconstructs valued living and self-as-context are investigated in this study. Valued living represents the action-focused component of *commitment* in ACT and was also reported to increase in people participating in the original group therapy program (Bowers et al., 2021). Self-as-context represents an ACT-specific conceptualization of the self. Self-concept was repeatedly demonstrated as an important determinant of mental health after brain injury (Ownsworth, 2014), yet self-as-context represents the so far least often investigated subconstruct of psychological flexibility in ACT research (Foote et al., 2023). Hence, we included these processes in this pilot study for the investigation of preliminary efficacy.

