## Study Design

The study employs a pre-post design without a control group. Consequently, there is no randomization or blinding to conditions. Group therapy is conducted with two groups, each consisting of six individuals. The therapy consists of 8 sessions, each lasting 90 minutes. A 30-minute diagnostic examination with questionnaires, including socio-demographic and health-related data, current psychopathology (depressive symptoms, PHQ-9; Kroenke et al., 2001; psychological burden, DASS-21; Lovibond & Lovibond, 1995; anxiety, GAD-7; Spitzer et al., 2006), and ACT-specific outcomes (valued living, VQ; Smout et al., 2014; psychological flexibility, AAQ-ABI; Sylvester, 2011; self-as-context, SACS; Zettle et al., 2018) takes place just before the first session. AAQ-ABI and SACS were translated into German for the first time according to recommendations using independent forward and backward translations (Wild et al., 2005). The questionnaires PHQ-9, DASS-21, GAD-7, AAQ-ABI, VQ, and SACS were also translated into plain language by a professional translation service ("Office for Easy Language Bethel", Bielefeld). After each session, participants and therapists rate the session using the GTS-P and the GTS-T, respectively. After the last session, all participants answer the same questionnaires as before the first session. They evaluate the entire therapy in the GTS-P and indicate if they would recommend the therapy to a friend with similar complaints (yes/no). The pre- and post-assessments are conducted by a trained assistant to exclude biases from the study therapists as facilitators. After the last session, therapists rate the entire therapy for each patient using the GTS-TP.

In a session form, therapists also record the participation of individual persons (Yes/No) and the completion of homework assignments (Yes/No/Incomplete) for each session. If not completed or incomplete, subjective obstacles are queried and documented. This serves to examine feasibility regarding session adherence and homework completion (objective 1).

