## Selection and Exclusion of Subjects

The participants are recruited through initial consultations at the university's neuropsychological outpatient clinic as well as through self-help groups and practitioners in the region involved in the aftercare of stroke survivors. For this purpose, information flyers are sent to neurological rehabilitation clinics as well as neurological, physiotherapy, occupational therapy, and speech therapy practices. Information and contact details for the study are also published on the homepage of the outpatient clinic and the research unit. Eligibility is evaluated by the principal investigator in an a-priori screening session using relative's information as additional source, if possible.

The study includes N = 12 adult individuals who:

1. have experienced a stroke (ischemic infarction or intracerebral hemorrhage);
2. report increased distress according to the DASS-21;
3. demonstrate sufficient cognitive and linguistic abilities; and
4. show sufficient motivation for therapy.

Increased distress according to the DASS-21 is defined as exceeding a cutoff on at least one of the three subscales of the questionnaire (Depression = D > 10, Anxiety = A > 6, and Stress = S > 10; Nilges & Essau, 2015). In the initial consultation, the cognitive and linguistic performance is assessed based on the participants' self-report and, if applicable, that of a family member, supplemented by the external judgment of the study leader, who has extensive experience in clinical work with individuals with brain damage. If the participant, possibly with input from a family member, and the study leader agree that the person can effectively participate in and benefit from 90-minute group therapy sessions on a weekly basis, the criterion is considered fulfilled. Finally, therapy motivation is assessed by participants assuring their willingness to change their approach to the illness, attend sessions regularly, and complete homework assignments within the therapy program as fully as possible.

Exclusion criteria are assessed based on self-report and external reports by the interested individual, the study leader, and possibly a family member, and include:

1. Interaction or behavioral disorders that significantly hinder group participation (e.g., significantly increased irritability or apathy);
2. Other severe psychiatric disorders (dementia, psychosis, personality disorder, intellectual disability); and

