## Assessment of Safety and Adverse Events

In the screening session, presence of dysphagia is assessed via self-report to consider and adjust provision of drinks and/or snacks during the group therapy for individuals with impaired swallowing functions. Regarding all other physical health risks, legal and university internal protective measures are followed.

Severe adverse events (SAEs) are recorded after half of the sessions (end of session 4) and after the last session. SAEs include unplanned admissions to psychiatric ward, severe self-mutilating behavior with threat to life, suicide attempts, and death. There is also space on the questionnaire to report further burdensome events. If participants miss a session without giving notice, therapists contact them or relatives via telephone to exclude SAEs. After reporting a SAE, a study therapist immediately counsels the participant on treatment options. In case of death, relatives are offered counseling. Reporting of an SAE leads to immediate pausing of the study. Each SAE is then reported to two psychotherapists who do not participate in facilitating the study therapy. They assess whether a causal relationship between the SAE and the intervention is probable. If a probable relationship is determined, the study is immediately terminated.

Adverse events (AEs) are defined as an increase in documented symptoms of depression, anxiety, and stress, or the emergence of new symptoms by the end of therapy. Participants experiencing new symptoms are offered counseling on further treatment options. During the group therapy, participants may always approach therapists to report increased burden. Therapists may also decide to address suspected increase of burden in individual participants. In case of increased burden, participants are offered counselling on treatment options.

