## Statistical Analysis Plan

Missing values are replaced by multiple imputation including all assessed variables. Outliers are identified by visual inspection and inclusion/exclusion is decided on a case-by-case approach. Estimates are calculated based on 95% confidence intervals.

Feasibility (research question 1) is assessed by frequencies fulfilling the predefined cut-offs (see objectives).

The acceptance score of  $> 2$  is evaluated by Wilcoxon-tests for one sample (one-sided) for all versions of the GTS (-P mean of single sessions and entire therapy, -T, and -TP). Significant changes in primary outcomes psychological flexibility (AAQ-ABI) and psychological burden (DASS-21) are assessed with Wilcoxon-tests for paired samples (one-sided);  $p$ -value is Bonferroni-adjusted ( $p = .025$ ). Significant changes in secondary outcomes valued living (VQ), self-as-context (SACS), depressive symptoms (PHQ-9), and anxiety symptoms (GAD-7) are assessed with Wilcoxon-tests for paired samples (one-sided);  $p$ -value is Bonferroni-adjusted ( $p = .0125$ ). Individual changes in primary and secondary outcomes are also based on reliable change indices with a significance level of  $\alpha = .90$  (one-sided).

Sensitivity analyses examine the influence of the baseline variables age, gender, kind of stroke (ischemia vs. hemorrhage), current use of prescribed psychotropic drugs (yes/no), previous mental disorder (yes/no), and previous use of psychotherapy (yes/no) on changes in primary and secondary outcomes. These bivariate associations are investigated by Pearson correlations (for continuous covariates) and Chi tests (for categorical covariates;  $p = .05$ , two-sided) using the difference scores of the outcomes. Likewise, associations between therapy acceptance and the changes in efficacy outcomes (AAQ-ABI, DASS-21, VQ, SACS, PHQ-9 and GAD-7) are exploratively analyzed.

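### The reliable change criterion is printed at an unusable level, has no stated category for reliable deterioration, and gives no chance benchmark for the number of improvers

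*Combined protocol and SAP*

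**What the plan says.** Individual change gets one sentence in the Statistical Analysis Plan: "Individual changes in primary and secondary outcomes are also based on reliable change indices with a significance level of" .90, one-sided. The sentence states no direction, no categories of change, no source for the reliability or standard deviation in the index, and no count expected when nobody changes.

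The surrounding text bears on how to read it:

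- The group tests on the same outcomes are one-sided. For the primary outcomes: "Significant changes in primary outcomes psychological flexibility (AAQ-ABI) and psychological burden (DASS-21) are assessed with Wilcoxon-tests for paired samples (one-sided"). The secondary outcomes, also tested one-sided, are listed as "Significant changes in secondary outcomes valued living (VQ), self-as-context (SACS), depressive symptoms (PHQ-9), and anxiety symptoms (GAD-7"). That makes two primary and four secondary outcomes.
- The Objectives section gives the hoped-for directions: lower psychopathology and "increasing of ACT-specific outcomes".
- Under Assessment of Safety and Adverse Events: "Adverse events (AEs) are defined as an increase in documented symptoms of depression, anxiety, and stress", or new symptoms, by the end of therapy. No threshold is attached.
- Under Study Design: "The study employs a pre-post design without a control group".
- Under Selection and Exclusion of Subjects: "The study includes N = 12 adult individuals who" meet four criteria, one of which is a score above a DASS-21 cut-off on at least one subscale.

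**The concern.** There are three linked problems.

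1. **The printed level.** A significance level of .90 cannot be applied as written. An analyst has to reinterpret it before computing anything.
2. **The direction.** A one-sided criterion, placed beside one-sided efficacy tests with stated improvement directions, most naturally identifies improvers only. A participant who worsens by the same margin would then be grouped with the unchanged. The adverse event definition covers part of this gap, for symptoms, but on a different scale: any increase counts there, whereas improvement must pass a reliability threshold. The two counts cannot be set side by side. AAQ-ABI, VQ and SACS are not named in that definition.
3. **The benchmark.** Without a control group, nothing in the data shows how many people would cross the threshold without treatment. A report that one or two participants reliably improved could be taken as a sign of efficacy when measurement noise alone would produce it.

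**Working it through.** **Inputs.** N = 12 (Selection and Exclusion of Subjects). Six outcomes: AAQ-ABI and DASS-21 primary; VQ, SACS, PHQ-9 and GAD-7 secondary (Statistical Analysis Plan). Level printed as .90, one-sided (same section). Up to 20% for "drop-out rates" is tolerated (Objectives). Assumed for the benchmark: no true change, normally distributed error and a correct standard error of the difference. The documents give no reliability figures with which to check the last of these.

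**Step 1: the printed level.** The .90 is an input, not a derived figure, so there is nothing to reproduce. The one-sided cut-off is z(1 - alpha).

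- alpha = .90 taken literally: z = -1.28. Expected number of unchanged participants flagged: 12 x .90 = 10.8.
- alpha = .10 (90% confidence): z = +1.28. This is the only workable reading and is used below.

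**Step 2: improvers from noise, per outcome.** The count is Binomial(12, .10).

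- Expected: 12 x .10 = 1.2
- P(at least 1) = 1 - .9^12 = .718
- P(at least 2) = .341
- P(at least 3) = .111
- P(at least 4) = .026

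Four is the smallest count whose tail probability is below 5%. At the tolerated drop-out limit, 12 x .80 = 9.6. With 10 completers the expectation is 10 x .10 = 1.0 and P(at least 1) = 1 - .9^10 = .65.

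**Step 3: all outcomes.** 12 x 6 = 72 classifications, and 72 x .10 = 7.2 false improvements expected. Expectations add, so this does not require independent scales.

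**Step 4: deteriorations without a planned category.** At the same cut-off in the other direction, noise gives 1.2 deteriorators per outcome. DASS-21, PHQ-9 and GAD-7 are symptom scales, where an increase would normally fall under the adverse event definition. That leaves AAQ-ABI, VQ and SACS: 12 x 3 = 36 classifications, and 36 x .10 = 3.6.

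**Step 5: what the deteriorated count does not correct.** Suppose regression to the mean shifts scores towards improvement by s standard errors of the difference. The size of s is an assumption; the documents give none. Then P(improve) = 1 - Phi(1.28 - s) and P(deteriorate) = Phi(-1.28 - s).

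| s | Improvers of 12 | Deteriorators of 12 |
|---|---|---|
| 0 | 1.2 | 1.2 |
| 0.25 | 12 x .151 = 1.8 | 12 x .063 = 0.75 |
| 0.5 | 12 x .217 = 2.6 | 12 x .037 = 0.45 |

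An excess of improvers over deteriorators can therefore arise with no treatment effect.

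**The case against.** The strongest reply is that the plan speaks of individual changes, not of improvers. Being one-sided may only fix the critical value at 1.28, which could then be applied in each direction. This stands to the extent that improvement-only counting is inferred and not written. It does not remove the need for a clarification, because under either reading the text does not settle whether deteriorators are counted.

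A reader might also infer that worsening would be reported nowhere, and that all 7.2 chance deteriorations over the six outcomes would go unseen. The documents do not support that. The adverse event definition counts any rise in depression, anxiety or stress symptoms, which is more sensitive than a reliable change threshold. Average worsening on the ACT scales could show in the planned estimates with 95% confidence intervals. What is missing is narrower: a planned individual-level deterioration category, most clearly for AAQ-ABI, VQ and SACS.

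A third point is that comparing improvers with deteriorators is not a clean benchmark, because entry requires a raised DASS-21 score. This is right. The comparison handles symmetric measurement noise only. Regression to the mean would act most directly on DASS-21 and plausibly on the correlated PHQ-9 and GAD-7.

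Finally, the section on Assessment of Efficacy concedes that efficacy cannot be adequately proved in this study and ties its indicators to statistically significant changes. No decision rule or sample size rests on the reliable change count. That lowers the severity but is no reason to leave the sentence as it is.

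**Conclusion.** The point holds in a limited form. The printed level is a definite error and must be restated before the analysis can be run. The lack of a stated category for reliable deterioration is real, although the improvement-only direction is the natural reading and not an explicit rule. No chance benchmark is given. At 10% one-sided, one or two improvers per outcome is what noise produces in 12 people, and a count below four does not exceed chance at 5%. These figures rest on no true change and a correct standard error. The second assumption is uncertain, because AAQ-ABI and SACS are newly translated into German and all six outcome questionnaires are used in plain-language versions. Severity is low: this is a supplementary analysis in a pilot study that already limits its efficacy claims.

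**What to change.** Replace the sentence in the Statistical Analysis Plan with wording such as:

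> Reliable change is classified at |RCI| > 1.28 (10% in each direction). For each of the six outcomes the numbers reliably improved, unchanged and reliably deteriorated are reported, alongside the number expected by chance (10% of those classified per direction; 1.2 of 12). The source of the reliability and standard deviation used for each scale is stated.

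Add one sentence of interpretation: the deteriorated count is a benchmark for measurement noise only; because participants are selected on DASS-21 cut-offs, regression to the mean can raise the improved count and lower the deteriorated count without any treatment effect, so the comparison is descriptive.

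The cost is a few sentences in the SAP. No new data, visits or participants are needed. This is a free improvement.

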## Assessment of Efficacy

Study design, sample size, and application of novel questionnaire versions do not allow to sufficiently prove efficacy of the treatment. However, first indicators of efficacy are investigated by pre-/post comparisons of psychological flexibility (AAQ-ABI) and psychological burden (DASS-21). As secondary outcomes, changes in valued living (VQ), self-as-context (SACS), depressive symptoms (PHQ-9), and anxiety symptoms (GAD-7) are examined. Statistically significant changes are considered indicators of efficacy. In addition, number of participants under the cut-offs on DASS-21 (D  $\leq$  10, A  $\leq$  6, S  $\leq$  10), PHQ-9 ( $\leq$  11), and GAD-7 ( $\leq$  11) before and after the therapy are assessed.

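### The reliable change index is given a one-sided significance level of α = .90, which is unworkable; it is very probably a 90% confidence level labelled as alpha, and no cut-off is printed

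*Combined protocol and SAP*

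**What the plan says.** The Statistical Analysis Plan adds an individual-level analysis to the group-level Wilcoxon tests: "Individual changes in primary and secondary outcomes are also based on reliable change indices". The only threshold given for it is in the same sentence: "reliable change indices with a significance level of $\alpha = .90$ (one-sided"). It covers the two primary outcomes (AAQ-ABI, DASS-21) and the four secondary ones (VQ, SACS, PHQ-9, GAD-7).

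The other levels in that section are conventional:

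- primary outcomes: "Bonferroni-adjusted ( $p = .025")
- secondary outcomes: "value is Bonferroni-adjusted ( $p = .0125")
- covariate associations: .05, two-sided
- interval estimates: "Estimates are calculated based on 95% confidence intervals"

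The intended direction of change is in Objectives: "Preliminary efficacy is evaluated both via reducing of psychopathological symptoms and increasing of ACT-specific outcomes".

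Neither the Statistical Analysis Plan nor any other section prints a critical value for the index, its formula, a reliability coefficient or the source of a standard deviation. The score limits for the DASS-21, PHQ-9 and GAD-7 under Assessment of Efficacy describe clinical status. They are not reliable-change thresholds.

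**The concern.** A significance level is the rate of false positives one is prepared to accept. Nobody would plan to accept 90%, and every other error level in the section is .05 or smaller. The figure looks like a confidence level entered under the wrong name.

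That .90 is not an error rate is easy to see. Which cut-off should replace it is less clear, because 90% confidence corresponds to 1.28 one-sided and to 1.645 two-sided. The choice decides how many participants are reported as reliably improved, and it applies to six outcomes. If it stays open until the data are in, it can be made with the results in view. Readers also need the true level to judge how many improvers chance alone would produce among 12 people.

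**Working it through.** **Inputs.** α = .90, one-sided (Statistical Analysis Plan). N = 12 (Selection and Exclusion of Subjects). Assumptions: the index is standard normal when there is no true change, and all 12 participants have both assessments. The probabilities of at least one or at least two also need independent participants.

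**Companion levels.** These reproduce exactly as error rates: .05/2 = .025 for two primary outcomes and .05/4 = .0125 for four secondary outcomes. The .90 comes with no derivation, so there is no figure to reproduce. What can be checked is the cut-off it implies.

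**Literal reading.** The one-sided cut-off is the z with upper-tail area .90, which is z = -1.28. Anyone who is unchanged, or who worsened by less than 1.28 standard errors of the difference, passes as improved. The expected number flagged with no true change is 12 × .90 = 10.8. Reading .90 as a two-sided α does not help: the cut-off is then |z| = 0.13.

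**Workable readings.** The upper-tail area is .10 for 90% one-sided confidence and .05 for 90% two-sided confidence (5% per tail). False classifications as improved, per outcome, with no true change:

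| | α = .10 per tail | α = .05 per tail |
|---|---|---|
| Cut-off | 1.28 | 1.645 |
| Expected, 12 × α | 1.2 | 0.6 |
| At least one, 1 − (1 − α)^12 | 1 − .90^12 = .718 | 1 − .95^12 = .460 |
| At least two, 1 − (1 − α)^12 − 12α(1 − α)^11 | .341 | .118 |

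Only the first column agrees with the printed sidedness.

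**From z to score change.** With the usual form of the index, the smallest change that counts is z × √(2(1 − r)) baseline SDs, where r is the reliability. The documents give no r, so .70 to .90 is an assumed range:

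- z = 1.28: 0.99 SD at r = .70, 0.57 SD at r = .90
- z = 1.645: 1.27 SD at r = .70, 0.74 SD at r = .90

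Over this range the reliability changes the threshold by a factor of 0.993/0.573 = 1.73. The choice between the two z values changes it by 1.645/1.282 = 1.28.

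**The case against.** The strongest reply is that this is an obvious labelling slip. A competent analyst would read 90% confidence, note the one-sided qualifier, arrive at 1.28 and never apply -1.28. A level of .90 is also not mathematically impossible, and the false-positive counts at 1.28 and 1.645 describe two coherent rules, not damage done by the misprint. All of this is fair. It is why the point is minor and why the level is called unworkable here. It does not remove the error: the only stated threshold is wrong as printed, nothing elsewhere corrects it, and the natural repair is an inference that the sponsor has to confirm.

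The counts are also nominal. Treatment is given in two groups of six with one therapist common to both (Study Design; Treatment of Subjects), so independence between participants is doubtful. This affects the probabilities of at least one or at least two, but not the expected 1.2 or 0.6. The per-person rate further depends on a correctly calibrated index. AAQ-ABI and SACS are first German translations, and all six scales are used in plain-language versions.

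Two smaller points also stand. Objectives gives the direction of improvement for the constructs, but the documents do not state how AAQ-ABI, VQ and SACS are scored, so the sign on raw scores has to be written down. And Assessment of Efficacy says "Statistically significant changes are considered indicators of efficacy" without naming the Wilcoxon tests. That the index is supplementary rests on its being introduced as an addition to those tests.

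**Conclusion.** The concern holds, as a minor one. The printed level cannot serve as a Type I error rate for this index. The best-supported reading is 90% one-sided confidence (α = .10, cut-off 1.28); the two-sided convention with 1.645 is possible but fits the text less well. Between them the expected number of false improvers per outcome halves from 1.2 to 0.6 of 12, and the chance of at least one falls from 72% to 46%, under the assumptions listed in the working.

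The Wilcoxon tests, their Bonferroni levels and the sample size are unaffected. Confidence in the error is high. The intended level is for the sponsor to confirm.

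**What to change.** Before analysis, replace the phrase in the Statistical Analysis Plan. If the sponsor confirms the best-supported reading: *α = .10, one-sided (90% one-sided confidence); reliable improvement is an index beyond 1.28 in the direction of improvement (symptoms down, ACT-specific outcomes up)*. If the two-sided 90% convention was intended, say so and print 1.645. Give the nominal expected number of false improvers per outcome with no true change: 1.2 of 12 at 1.28, or 0.6 of 12 at 1.645.

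This costs one sentence, needs no new data and leaves the Wilcoxon tests as they are. It settles only the z cut-off. To make the index reproducible, print beside it the formula, the reliability and SD source for each scale version used, and the scoring direction of each scale.

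Reliable deterioration could be reported with the same index; this is optional and not a correction. At 1.28 the combined rate with no true change would be 2 × .10 = .20, or 12 × .20 = 2.4 of 12 per outcome, with a 1 − .80^12 = 93% chance of at least one classification in either direction. Assessment of Safety and Adverse Events already counts "an increase in documented symptoms of depression, anxiety, and stress" as an adverse event, without a reliable-change threshold.

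### The block called sensitivity analyses is 36 unadjusted covariate-by-outcome tests in 12 people, and 30 of them use a Chi2 test that does not fit a change score

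*Combined protocol and SAP*

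**What the plan says.** Selection and Exclusion of Subjects fixes the sample: "The study includes N = 12 adult individuals who" meet four inclusion criteria.

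The last paragraph of the Statistical Analysis Plan begins "Sensitivity analyses examine the influence of the baseline variables age, gender, kind of stroke". Its full list of baseline variables is "age, gender, kind of stroke (ischemia vs. hemorrhage), current use of prescribed psychotropic drugs (yes/no") and "previous mental disorder (yes/no), and previous use of psychotherapy (yes/no"). Their influence is examined "on changes in primary and secondary outcomes". There are two primary outcomes (AAQ-ABI, DASS-21) and four secondary ones (VQ, SACS, PHQ-9, GAD-7).

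Continuous covariates get a Pearson correlation and categorical covariates a Chi2 test, at p = .05, "two-sided) using the difference scores of the outcomes". The plan does not say how a difference score becomes a category for the Chi2 test. It states no adjustment for this block, although the paragraph before it adjusts the primary tests to .025 and the secondary tests to .0125.

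The next sentence adds "associations between therapy acceptance and the changes in efficacy outcomes" and describes that analysis as explorative. The word is not applied directly to the covariate tests.

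**The concern.** There are two problems, and the second decides how large the first is.

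**Label and threshold.** A sensitivity analysis asks whether a result survives other assumptions, for example on missing data or outliers. These tests do not revisit the pre-post result. They relate baseline characteristics to the amount of change, which is a search for modifiers. In the same section, families of two and four tests are corrected and a family of 36 is not.

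**Choice of test.** A difference score on these questionnaires is a quantity with many possible values. A Chi2 test ignores its order and needs categories, which the plan does not define. Depending on how the analyst fills the gap, 30 of the 36 tests either can hardly reject or reject at a rate set by choices that could be made after seeing the data.

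At stake is a misleading statement in either direction: a chance finding reported as an influence on treatment response, or a non-significant result reported as no influence when the test had almost no means of showing one.

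**Working it through.** **Inputs from the documents.** N = 12. Six covariates: one continuous (age) and five categorical. Six outcomes: two primary and four secondary. Two-sided .05 per test.

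**Assumptions, because the plan is silent.** DASS-21 counts as one score; with its three subscales there would be 8 outcomes and 6 × 8 = 48 tests. Gender is taken as two-level. All 12 people have both assessments. The correlation among the six change scores is varied.

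**The plan's own multiplicity figures.** .05/2 = .025 and .05/4 = .0125. Both are exact for their families. The plan gives no figure for the covariate block.

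**Step 1: nominal figures, if every test had a true size of 5% and no association existed.**
- Tests: 6 × 6 = 36, of which 6 are Pearson and 5 × 6 = 30 are Chi2.
- Expected false positives: 36 × .05 = 1.8.
- At least one, if independent: 1 − .95^36 = 84.2%.
- At least one, with correlated change scores (simulated): about 82% at correlation .3, 76% at .5, 69% at .7 and 53% at .9. The expected number stays at 1.8.

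**Step 2: the six age correlations.** These are ordinary .05 tests under any reading.
- Expected false positives: 6 × .05 = 0.30.
- At least one: 1 − .95^6 = 26.5% if independent; about 22% at correlation .5 (simulated).
- Smallest significant correlation: t(.975, 10 df) = 2.228, so |r| = 2.228/√(10 + 2.228²) = .576.
- A true r of .30 would be significant about 16% of the time, and the significant estimates would average about .67 in absolute size (simulated).

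**Step 3: the 30 Chi2 tests on raw difference scores.** In a table with two rows, Pearson's chi-square cannot exceed N = 12. An outcome with k distinct change values has k − 1 degrees of freedom.

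| Distinct values | df | .05 critical value | p at the maximum of 12 |
|---|---|---|---|
| 6 | 5 | 11.07 | .035 |
| 7 | 6 | 12.59 | .062 |
| 12 | 11 | 19.68 | .364 |

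From seven distinct values on, no data can give p < .05. With 12 distinct values the statistic is always exactly 12 and p is always .36.

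**Step 4: the 30 Chi2 tests on grouped scores.** In a 2 × 2 table with 12 people, even the most balanced margins give expected counts of 6 × 6/12 = 3. The usual minimum of 5 in every cell cannot be met.

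**Step 5: the whole block of 36 under each reading.** Simulated with no true association, N = 12, change-score correlation 0 and .5, and level prevalences between .2 and .4 (.4 only for the SD 1.5 row). The SDs of change are assumed.

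| Reading of the Chi2 tests | Expected false positives | At least one |
|---|---|---|
| Raw integer scores, SD 5 to 8 points | about 0.3 | 21–29% |
| Raw integer scores, SD 3 | 0.4–0.5 | 30–39% |
| Raw integer scores, SD 1.5 | about 0.9 | 55–58% |
| Median split, no continuity correction | about 2.2 | 79–89% |
| Median split, Yates correction | 0.4–0.5 | 29–37% |

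In the first row almost all false positives come from age; the 30 Chi2 tests together contribute about 0.01 or less at prevalence .4.

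**The case against.** A reader might infer from 36 tests at .05 that at least one false influence is the expected result. The documents do not support that. It needs a size of about 5% in all 36 tests, and 30 of them are Chi2 tests whose size the plan leaves open. On raw scores with a change SD of 3 points or more, or on a Yates-corrected median split, the likelier outcome is no false positive. The 1.8 and 84% are nominal figures.

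A reader might also infer that these results will shape eligibility for a later trial. Nothing in the documents says so, and none of the three research questions under Objectives concerns who benefits. Assessment of Efficacy also concedes that design and sample size cannot sufficiently prove efficacy.

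Three further points have weight. Leaving ancillary associations in an uncontrolled pilot unadjusted is common and defensible when they are labelled as such. The sentence on acceptance opens with a word that may tie it to the covariate tests, so the explorative label could be read as covering both, although the text is ambiguous. And the section says in general terms that estimates rest on 95% confidence intervals, so interval reporting is partly planned.

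These points limit the size of the problem. They do not explain why a Chi2 test is applied to a quantitative change score, or how the scores are to be grouped. Nor do they make the block a test of robustness.

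**Conclusion.** The point holds in a limited form. The plan sets 36 unadjusted .05 tests in 12 people under a label that does not describe them. For 30 of these tests the named method does not suit the data and is under-specified. The chance of at least one false positive runs from about 21% to 89% over the Chi2 readings examined; that width comes mainly from what the plan leaves open. The six age correlations alone give about 22–27%.

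The small sample does not raise the false-positive count of a correctly sized test. It means that a significant age correlation must be at least .576 in absolute size and so is likely to overstate a modest true one. It also makes the Chi2 approximation unreliable.

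The counts and the bound of 12 follow from the documents, taking two-level covariates and complete data. The simulated ranges also rest on the assumed SDs, prevalences and correlations. The analyses are ancillary, so neither the feasibility and acceptance results nor the primary pre-post tests are affected. The correction should be made because it is cheap and works under every reading.

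**What to change.** In the Statistical Analysis Plan:
- Rename the block exploratory associations and drop the wording about influence.
- Replace the Chi2 tests with the Hodges-Lehmann difference in change between the two levels, with a 95% interval. If a covariate has more than two levels, state beforehand which contrast is reported.
- Report age as a correlation with the change score, with a 95% interval.
- Report all 36 estimates and make no significance claim. If p-values are shown, state that they are unadjusted and that 36 tests were run.
- State whether DASS-21 enters as one score or three subscales, and correct the count if it is three.

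A formal correction over all 36 is not needed. Bonferroni would require .05/36 = .00139 per test, or |r| of about .81 at N = 12, which has little practical use here.

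The cost is wording and a small change to the analysis code; no new data or visits are needed. The downside is that no covariate can be declared significant, which 12 people could not support anyway.
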